5.5.2 Duration of Effect

Duration of treatment effect will be evaluated by treatment group by assessing the following two variables.

[figure not shown]
- Time between study drug injection (injection) and patient's first request for retreatment

[figure not shown]
- Time between study drug injection (injection) and qualification for retreatment (study exit date for patients that requested and qualified for retreatment)

Patients who did not request retreatment will be treated as censored at the time of study exit.

For each treatment group, the Kaplan-Meier survival methodology will be used to estimate the median time to request for re-treatment. Furthermore, the 25th and 75th percentiles of the time to request for re-treatment will be estimated. The associated 95% CIs will also be presented for each treatment group. The proportion of patients requesting re-treatment during the study will also be presented.

The time to qualification for re-treatment will be summarized in a similar manner.

A horizontal bar chart with 10 bars. The bars are black and vary in length. The first bar is the longest, followed by a short bar, then a long bar, then a short bar, then a long bar, then a short bar, then a long bar, then a short bar, then a long bar, and finally a short bar. The bars are separated by thin white lines.

6.2 Adverse Events

[figure not shown]
Adverse events (AEs) will be coded by system organ class and preferred term using the Medical Dictionary for Regulatory Activities (MedDRA).

[figure not shown]
Pre-treatment AEs are AEs that have start date on or after the signing of consent form and prior to the BOTOX injection.

[figure not shown]
An AE will be considered a treatment-emergent adverse event (TEAE) if it was present after the first dose of study treatment or was present before the date of the first dose of study treatment and increased in severity or became serious after the first dose of study treatment.

[figure not shown]
The number and percentage of patients reporting TEAE in each treatment group will be tabulated by descending percentage in any group, by system organ class and preferred term, and further categorized by severity and causal relationship to the study drug and study drug injection procedure. If more than 1 AE is coded to the same patient, the patient will be

[figure not shown]
counted only once for that preferred term using the greatest severity for the summarization by severity and causal relationship.

[figure not shown]

[figure not shown]
[figure not shown]

[figure not shown]

9. Interim Analyses

No interim analysis is planned for this study. However, there is a Data Review Committee (DRC) that reviews, on regular bases, selected blinded safety analyses. There is a separate DRC charter and analysis plan that outlines the function of the DRC and what they will be reviewing.

10. Analysis for US FDA

Not applicable.

11. Data Collected but not Analyzed

A patient's surgical history and female patients' birth control treatment during the study are collected in this study. No output will be generated for these data.

12. Deviations from Protocol

There are no deviations from the protocol.

13. References

Mallinckrodt CH, Clark WS, David SR (2001a). Type I error rates from mixed-effects model repeated measures versus fixed effects analysis of variance with missing values imputed via last observation carried forward. *Drug Information J*. 2001a;35:1215-1225.

Mallinckrodt CH, Clark WS, David, S. R. (2001b). Accounting for dropout bias using mixed-effects models. *J. Biopharmaceutical Statistics*. 2001b;11:9-21.

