## **5.9 Treatment Administration**

### **5.9.1 Day of Treatment Criteria**

The following “day of treatment criteria” must be fulfilled prior to the administration of study medication:

- patient does not have a UTI, in the opinion of the investigator (taking into account patient symptoms, presence of significant leukocyturia at screening (e.g.  $\geq 30$  WBC/HPF), urine culture results, need for antibiotic treatment, etc)
- appropriate prophylactic antibiotics have been initiated (see Section 5.9.2)
- antiplatelet or anticoagulant therapy or medications with anticoagulative effects have been discontinued at least 3 days prior to treatment
- negative urine pregnancy result (for postmenarche females)
- investigator continues to deem treatment is appropriate and no condition or situation exists which, in the investigators opinion, puts the patient at significant risk from receiving treatment

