## 5.9.2 Prophylactic Antibiotics

All patients must receive prophylactic antibiotics prior to treatment administration on randomization/day 1.

The approach is dependent upon the clinical judgment of the investigator, but could include either an intravenous (IV) dose of antibiotics prior to treatment administration on day 1 or oral antibiotics for at least 1 to 3 days prior to treatment and on the day of treatment.

Antibiotics could also be continued for 1 to 3 days posttreatment (or longer).

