## **6.3 Examination Procedures, Tests, Equipment, and Techniques**

Screening procedures can commence once the parental/legal guardian consent, minor assent, and data authorization/protection forms have been obtained; screening will be considered to have started (eg, day -28) at the time of the first screening activity or procedure. On completion of screening, when all the required inclusion/exclusion and “day of treatment criteria” have been met, the patient will be randomized (day 1) and considered enrolled in the study.

Evaluations should be performed by the same evaluator throughout the study whenever possible. If it is not possible to use the same evaluator to follow the patient, then it is preferable to have the evaluations overlap (examine the patient together and discuss findings) for at least one visit.

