## 9.1 Definitions

### 9.1.1 Adverse Event

Any untoward medical occurrence in a patient or clinical investigation patient administered a pharmaceutical product and that does not necessarily have a causal relationship with this treatment. An adverse event can therefore be any unfavorable and unintended sign (including an abnormal laboratory finding), symptom, or disease temporally associated with the use of a medicinal (investigational) product, whether or not related to the medicinal (investigational)

product. In addition, during the screening period, adverse events will be assessed regardless of the administration of a pharmaceutical product.

Note: Adverse events must be collected once informed consent has been obtained, regardless of whether or not the patient has been administered study drug.

Progression of NDO, including new or worsening of anticipated clinical signs or symptoms, which are collected as clinical efficacy variables and assessed as unequivocally associated with the disease progression and /or lack of efficacy, should not be reported as adverse events unless the disease progression is greater than anticipated in the natural course of the disease.

Adverse events will be assessed, documented, and recorded in the eCRF throughout the study (ie, after informed consent/assent has been obtained). At each visit, the investigator will begin by querying for adverse events by asking each patient or parent/caregiver a general, non-directed question such as “How have you been feeling since the last visit?” Directed questioning and examination will then be done as appropriate. All reported adverse events will be documented on the appropriate eCRF.

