2.3 Data Conventions

The following data conventions will be applied to all analyses.

- A patient's weight adjusted dose will be derived using the randomization information and the patient's actual weight provided in IVRS/IWRS at baseline.
- Unless stated otherwise, all statistical tests will be at a 2-sided significance level of 0.05. P-values ≤ 0.050 will be considered statistically significant.
- Since the qualification for retreatment may occur anytime from week 12 onwards, no statistical tests for pairwise comparison of treatment groups will be performed for any visit beyond week 12.
- The type III sums of squares will be used for all analysis of covariance models (ANCOVA).
- The variance for Kaplan-Meier estimates will be calculated using Greenwood's formula.
- Descriptive statistics for continuous variables include the sample size (N), mean, SD, median, minimum (min), first quartile (Q1), third quartile (Q3), and maximum (max).

- Summary statistics for categorical variables include the sample size (N), frequency count and percent.
- The Medical Dictionary for Regulatory Activities (MedDRA) dictionary will be used to code all adverse events (AEs) and medical history.
- World Health Organization Drug Dictionary Enhanced (WHO DDE) preferred name and MedDRA will be used to code all medications.
- Study duration from day 1 (injection date) will be calculated as:

Study day in study = visit date – day 1 date + 1.

- For vital signs and laboratory summary tables, baseline is defined to be the last assessment prior to BOTOX injection.
- For by visit, vital signs and laboratory summary tables, there will also be a summary of the last post-baseline assessment.
- The algorithm presented in [Table 3](#), together with the rules below will be used to impute incomplete or missing dates for adverse events and medications as follows:
 - (a) AE start dates will be imputed as the minimum of the following:
 - initial imputed date, where target date = study drug injection date
 - complete end date
 - (b) Medication start dates will be imputed as the minimum of the following:
 - initial imputed date, where target date = study drug injection date – 1
 - complete end date
 - (c) AE and Medication end dates will be imputed as the minimum of the following:
 - initial imputed date, where target date = study exit date + 30
 - death date

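### As worded, the SAP's TEAE definition tests whether an event was present after dosing, not when it began, so unchanged screening-period events would count as treatment-emergent

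*SAP*

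**What the plan says.** SAP 6.2 gives two alternative routes to treatment-emergent status. The first is: "An AE will be considered a treatment-emergent adverse event (TEAE) if it was present after the first dose of study treatment". The second, joined by *or*, covers an event that "was present before the date of the first dose of study treatment and increased in severity or became serious after the first dose". TEAEs are then tabulated by treatment group, system organ class and preferred term, and further by severity and causal relationship.

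The same section has a separate pre-treatment class: "Pre-treatment AEs are AEs that have start date on or after the signing of consent form and prior to the BOTOX injection". That class goes by start date and does not require the event to have resolved before injection.

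Three other places bear on the point:

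- Protocol 9.1.1, on when collection begins: "Adverse events must be collected once informed consent has been obtained, regardless of whether or not the patient has been administered study drug".
- Protocol 6.3, on how early screening can begin: "screening will be considered to have started (eg, day -28) at the time of the first screening activity or procedure".
- SAP 2.3, on incomplete AE start dates, which take the earlier of the complete end date and the "initial imputed date, where target date = study drug injection date".

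**The concern.** Being present after a dose is not the same as starting after it. Events are collected from consent, and screening may open weeks before injection, so some patients can reach day 1 with an adverse event already recorded and still ongoing. If nothing about that event changes, it is not what a treatment-emergent table is meant to show. The first limb nevertheless admits it.

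Safety is a stated objective, and this trial has no untreated control group, so the by-dose TEAE percentages are a main part of the safety evidence. An analysis plan is also a programming specification. One programmer following the sentence literally and another inferring the usual meaning could produce different tables from the same data.

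**Working it through.** The plan gives no figure to reproduce, so the check is mainly one of logic.

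**1. Literal rule against an onset rule.** Let A = present after the dose, B = present before the dose, C = worsened or became serious after the dose.

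- Literal rule (SAP 6.2): TEAE = A or (B and C).
- Onset rule: TEAE = (started at or after injection) or (B and C).

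| Event | Literal | Onset rule | Pre-treatment class |
|---|---|---|---|
| Began before dose, resolved before dose | no | no | yes |
| Began before dose, continues unchanged | **yes** | **no** | yes |
| Began before dose, continues and worsens or becomes serious | yes | yes | yes |
| Began after dose | yes | yes | no |

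The rules differ in one row only: the unchanged carry-over event.

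**2. Redundancy.** An event that worsens or becomes serious after the dose is necessarily present after it, so (B and C) implies A. Under the literal rule the second limb never adds an event.

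**3. Size in a preferred-term row.** One carry-over patient with no new event of that term adds 100/n percentage points. The safety groups follow dose received (SAP 2.1), so n is not fixed in advance and is assumed here:

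- n = 20: 100/20 = 5.0
- n = 30: 100/30 = 3.3
- n = 40: 100/40 = 2.5
- n = 50: 100/50 = 2.0

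**4. Size in the any-TEAE row.** The documents give neither TEAE rates nor carry-over rates. To see whether a useful bound exists, assume true rates of 40% and 55% (difference 15.0 points) and carry-over in 10% of patients in each group. The result depends on how carry-over overlaps with true TEAEs:

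- Independent, shown rate = p + (1 − p)q: 0.40 + 0.60 × 0.10 = 46.0%; 0.55 + 0.45 × 0.10 = 59.5%; difference 13.5.
- Every carry-over patient also has a true TEAE, in both groups: 40 v 55; difference 15.0.
- No carry-over patient has one, in both groups: 50 v 65; difference 15.0.
- No overlap in the first group, full overlap in the second: 50 v 55; difference 5.0.
- Full overlap in the first group, none in the second: 40 v 65; difference 25.0.

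The last two are extreme, but they show that the effect on a dose difference cannot be bounded tightly from the documents, even with rates assumed.

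**5. What rewording the first limb alone would do.** The second limb requires presence before the *date* of the dose. Activity on day 1 precedes injection. For example, Protocol 5.9.2 says: "All patients must receive prophylactic antibiotics prior to treatment administration on randomization/day 1". That sentence does not mention adverse events, but it shows that a day-1 event could start before injection. If such an event then worsened, it would fail a first limb based on onset (it began before injection) and also fail the second limb (it was not present before that date). The present text has no such gap, because the first limb catches everything. The gap would appear only on correction, so both limbs need to change together.

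**6. Imputed dates.** SAP Table 3 gives an event known only to have begun in the month and year of injection the injection date itself, subject to the earlier-of rule with a complete end date. A blanket rule that every such event is a TEAE would readmit a carry-over event whose record shows by other means that it began in screening.

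**The case against.** The strongest reply is that context settles the meaning. The second limb is pointless unless the first means new events, the neighbouring definition sorts by start date, and imputation is anchored on injection. A programmer reading the whole section would probably apply an onset rule. This stands as evidence of intent. It makes the point a drafting defect, not a deliberate choice to count carry-over events.

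The readable text is also incomplete. The SAP's amendment log names a section 6.2.1 whose text is not visible, and most of Protocol 7.4 is redacted. An onset convention could sit in either place. That stands too, although the visible sentence would still need to agree with it.

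A reader might infer that overlap between the pre-treatment and treatment-emergent classes is itself an error. The documents do not support that. Nothing visible makes the classes exclusive, and SAP 2.3 lets one medication be both prior and concomitant.

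The practical scope is also limited. Carried-over urinary tract infection should be uncommon, because injection requires that the "patient does not have a UTI, in the opinion of the investigator". Any miscount adds events and does not remove them.

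**Conclusion.** The point holds as a minor wording defect. In the readable text, the TEAE definition has no onset condition. Followed literally, it counts unchanged screening-period events that persist past injection, and its worsening limb is redundant. New onset was very probably intended.

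The effect is confined to the by-dose TEAE tables, and efficacy is unaffected. Its size cannot be estimated from the documents. The one simple scale is 100/n points for each carry-over patient in a preferred-term row, about 3.3 at an assumed n = 30.

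A reader might go further and infer that the TEAE tables will be wrong, or that dose comparisons will be biased or only slightly diluted. None of these follows. The first assumes literal programming and that such events exist. The others depend on carry-over rates and overlap patterns that the documents do not give. If carry-over is unrelated to dose and overlaps with true TEAEs alike in each group, it creates no spurious dose difference in expectation. A single patient can still move a small row by chance.

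**What to change.** Three changes to SAP 6.2:

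1. In the first limb, replace the presence test with *started at or after study drug injection*.
2. In the second limb, refer to presence *before the first dose*, not before its date, so that a day-1 event that begins before injection and then worsens is still counted.
3. Add one day-1 rule: *an adverse event of unknown timing on the day of injection, or with a start date imputed to the injection date, is a TEAE unless the recorded information shows that it began before injection; in that case it is a TEAE only if it worsened or became serious afterwards.*

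If text that is not visible already contains an onset rule, align the definition in 6.2 with it.

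The cost is a short wording amendment and the matching line in the programming specification. No new data and no design change are needed. No event is lost from reporting, because unchanged carry-over events remain in the pre-treatment class.

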With respect to safety, adverse events were primarily limited to local adverse events related to the urinary tract, in particular urinary retention and urinary tract infection (UTI). In patients not using CIC prior to treatment, a dose-dependent increase in post-void residual urine volume was observed posttreatment. A proportion of patients, both in the placebo and active dose groups, initiated CIC that was also dose-dependent.

A consistent efficacy and safety profile has been demonstrated with repeat BOTOX treatment. The reductions from baseline in urinary incontinence episodes remained similar

over repeated BOTOX treatments, as did the improvement in HRQOL. The most common adverse events remained urological (eg, urinary tract infection and urinary retention), and the incidence of such adverse events did not increase with repeated BOTOX treatment.

Since there was no additional efficacy or benefit with the 300 U BOTOX dose compared to the 200 U BOTOX dose, and given that the 200 U BOTOX dose displayed a better safety profile, 200 U BOTOX was submitted for licensing registration, and approval has subsequently been granted in many countries at this dose.

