## 7.7 Sample Size Calculation

The sample size calculation for this study is determined empirically, while taking into account the treatment effect observed in the adult pivotal phase 3 studies, 191622-515 and 191622-516. The mean (standard deviation) of the change from baseline in daily urinary incontinence at week 6 was -3.1 (3.44) and -3.1 (2.58) in Studies 191622-515 and 191622-516, respectively.

Approximately 34 patients per treatment group are to be enrolled for the study. This includes 30 patients per treatment group and an increase to 34 per group in order to address patient attrition (estimated to be 10% by week 6)

The following table displays estimates of the distance for treatment differences between BOTOX 200 U (maximum 6 U/kg) and 50 U (maximum 6 U/kg) in mean daily average frequency of daytime episodes of urinary incontinence change from baseline at week 6 for a range of common standard deviations (SD). All calculations assume 30 patients per treatment group and a 2-sided test significance level of 0.05. The calculation was performed using the commercial software nQuery Advisor (procedure MTC0-1), version 6.01, and the CI is based on the large sample z statistic.

Standard Deviation	Distance From Mean to the Limit
2.0	1.012
2.5	1.265
3.0	1.518
3.5	1.771
4.0	2.024

Note: The ranges of the SDs are determined based on the values from the adult pivotal phase 3 studies (191622-515 and 191622-516). The estimate of the SD for the 200 U BOTOX treatment group is 3.44 for Study 191622-515, 2.58 for Study 191622-516, and 3.10 for the 2 studies combined.

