### **9.1.4        Severity**

A clinical determination will be made of the intensity of an adverse event. The severity assessment for a clinical adverse event must be completed using the following definitions as guidelines:

Mild	Awareness of sign or symptom, but easily tolerated.
Moderate	Discomfort enough to cause interference with usual activity.
Severe	Incapacitating with inability to work or do usual activity.
Not applicable	In some cases, an adverse event may be an 'all or nothing' finding which cannot be graded.

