### **9.1.5 Relationship to Study Drug or Study Procedure**

A determination will be made of the relationship (if any) between an adverse event and the study drug or study procedure, as applicable. A causal relationship is present if a determination is made that there is a reasonable possibility that the adverse event may have been caused by the drug or study procedure.

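### SAP 6.2 lets the most severe event decide causality too, so a patient with a milder related event and a worse unrelated event of the same term is shown as not related

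*SAP*

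**What the plan says.** SAP 6.2 counts patients with treatment-emergent events by system organ class and preferred term, "further categorized by severity and causal relationship to the study drug and study drug injection procedure". The rule for repeat events opens with "If more than 1 AE is coded to the same patient, the patient will be" and goes on to say that the patient is "counted only once for that preferred term using the greatest severity for the summarization by severity and causal relationship". Read together, the trigger is more than one event under the same preferred term.

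The protocol collects causality for each event. Section 9 puts severity and relationship on the adverse event form, and Section 9.1.5 states: "A determination will be made of the relationship (if any) between an adverse event and the study drug or study procedure, as applicable".

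Severity (Protocol 9.1.4) is mild, moderate or severe, plus a Not applicable category for an all-or-nothing "finding which cannot be graded". Neither document says where that category ranks.

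The visible parts of SAP 6.2 and Protocol 7.4 contain no closest-relationship or any-related rule, and no rule for two events of equal severity.

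**The concern.** Severity and causality are separate attributes of an event, and the worst event need not be the related one. Take a child with a mild urinary tract infection soon after injection, judged related to the procedure, and a moderate one months later, judged unrelated. The rule keeps the second event. The child is counted once, as moderate and not related, and the related infection is missing from the causality table. One selected event supplies both the drug and the procedure attribution, so either can be lost.

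Repeat events of one term are foreseeable here. Follow-up runs up to 48 weeks for patients who do not qualify for retreatment earlier. Protocol 6.3.2 records the number of urinary tract infections in the 6 months before screening, and SAP 4.2 summarises it. Of repeat treatment in the adult programme, Protocol Section 1 says: "The most common adverse events remained urological (eg, urinary tract infection and urinary retention").

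An acceptable safety profile is one of the two clinical hypotheses (Protocol 2.2). Groups are small, so one patient moved from related to not related is visible in a group percentage.

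**Working it through.** The plan gives no figure on this point, so there is nothing to reproduce. The check has two parts: what the rule does to each possible pair of events, and how large the loss could be under stated assumptions.

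**1. What the rule does**

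Take one patient with two events of one preferred term. Each event has severity 1 to 3 and is related or not related. That gives 3 × 2 × 3 × 2 = 36 ordered combinations. Causality differs between the two events in 2 × 9 = 18 of them. Under the written rule:

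- in 6 of the 18 the unrelated event is worse, and the related event is lost;
- in 6 the related event is worse, and it is kept;
- in 6 the severities are equal, and the SAP does not say which event is used.

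In the other 18 combinations causality agrees and nothing changes. No combination turns a patient without a related event into a related one, so the error runs in one direction only. If a patient counts as related when any event of the term is related, none of the 18 discordant combinations loses the related event.

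These are counts of combinations, not probabilities. Events graded Not applicable lie outside the enumeration because they have no rank.

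**2. Size under stated assumptions**

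From the documents: n = 34 per group. Protocol 7.7 says: "Approximately 34 patients per treatment group are to be enrolled for the study".

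Assumed, because the documents do not give them:

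- m = share of patients in a group with two events of one term at different severities, 5% to 20%;
- p = probability that an event is judged related, 0.1 to 0.5, independent of severity and of the patient's other event.

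A related patient is lost when the milder event is related (p) and the worse one is not (1 − p). Expected loss per group and term is therefore n × m × p × (1 − p):

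| m | p = 0.1 | p = 0.5 |
|---|---|---|
| 5% | 34 × 0.05 × 0.09 = 0.15 | 34 × 0.05 × 0.25 = 0.43 |
| 10% | 34 × 0.10 × 0.09 = 0.31 | 34 × 0.10 × 0.25 = 0.85 |
| 20% | 34 × 0.20 × 0.09 = 0.61 | 34 × 0.20 × 0.25 = 1.70 |

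Each lost patient is 1/34 = 2.9 percentage points of a group.

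Among patients who have such a pair and at least one related event, the share lost is 1 − p/[1 − (1 − p)²]. This is 47% at p = 0.1, 41% at p = 0.3 and 33% at p = 0.5. These shares do not apply to patients with a single event of a term, who are counted correctly.

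**The case against.** **Another reading.** The sentence could mean that events are first split by relationship and the worst is then taken within each category, in which case no related patient is lost. The wording is loose enough to allow this; its trigger, for instance, omits the preferred-term condition that is clearly meant. It is the less natural reading, though, and if it is the intended one the SAP should say so.

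**Unseen text.** Parts of SAP Section 6 and Protocol 7.4 are not visible, and the SAP amendment summary shows that a Section 6.2.1 exists. A separate table restricted to related events may be there. It would lessen the effect, but this sentence would still give a different count.

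**Size.** A reader might infer a large under-count, for example one fifth of patients with a related urinary tract infection. That takes inputs such as 14 of 34 patients affected, 5 of them twice, and p = 0.3. The true expectation is then 9 × 0.3 + 5 × 0.51 = 5.25 patients against 14 × 0.3 = 4.2 shown, a 20% loss. None of those inputs is in the documents, and the result also assumes that severity ties are broken without regard to causality. If ties go to the related event, the loss is 5 × 0.21 × (1 − t), where t is the tie probability: 0.70 patients (13%) at t = 1/3 and 0.53 (10%) at t = 1/2. If one child's events tend to receive the same causality judgement, it is smaller again.

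**Use of the table.** A reader might also infer that labelling, or a test of dose-related safety, rests on this table. The visible text supports neither: the listed safety measures are adverse events and serious adverse events, and no related-event endpoint or test appears. The under-count could differ by dose if children on one dose stay in the study longer, but that is conjecture.

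The objections on size and use stand. The objection to the finding itself does not: the visible rule names one selection key and applies it to causality.

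**Conclusion.** The rule is wrong as written for the causality summary. It can hide a related event behind a worse unrelated event of the same term, it cannot do the reverse, and it leaves equal-severity and ungraded events without a rule. The error is confined to patient counts by relationship within a preferred term. The events stay in the data.

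How many patients would be affected cannot be determined from the documents, and it is none if no patient has such a pair. The range of about 0.15 to 1.7 patients per group per term rests on the assumed m and p, on independence, and on 34 patients per group. It should be read as an order of magnitude. The point deserves correction because the rule gives a wrong count and is cheap to fix, not because a large bias has been shown.

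**What to change.** Replace the counting sentence in SAP 6.2 with:

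> A patient is counted once per preferred term. For the severity summary, the event of greatest severity is used. For the causal-relationship summaries (study drug and injection procedure, separately), the patient is counted as related if any event of that term was judged related.

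This removes the dependence on severity from the causality tables and so settles ties and ungraded events there. Ties do not matter in the severity summary, but a short clause should say how Not applicable events are shown in it.

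The cost is one SAP sentence and a small change to the programmed selection rule, with no new data. Reported percentages of patients with related events may be slightly higher. If a related-only table already exists elsewhere in Section 6, the new sentence should be checked against it so that both give the same counts.
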